**STUDY PROTOCOL****Prospective Multicenter Study on Localization Accuracy and Clinical Utility of Automated Electric Source Imaging in Presurgical Evaluation( PROMAESIS)**

Brief Title: Clinical Utility of Automated Electric Source Imaging in Presurgical Evaluation (PROMAESIS)

Identifiers: NCT04218812; Unique Protocol ID: PROMAESIS

Date: August 8, 2018

*Goal:* to elucidate the accuracy and the clinical utility of automated electric source imaging (ESI) in presurgical evaluation.

*Primary outcome:* accuracy measures (sensitivity, specificity, positive and negative predictive values), overall accuracy (number of [TP and TN]/total patients).

*Secondary outcomes:* clinical utility (change in patient management decisions); inter-ESI-methods agreement (at sub-lobar level).

*Patients:* consecutive patients will be prospectively recruited from the EpiCare and E-epilepsy centers.

Inclusion criteria: patients with drug resistant focal epilepsy, admitted to EMU for presurgical evaluation, who are afterwards discussed at the multidisciplinary epilepsy surgery team meetings. Exclusion criterion: patients who did not have a seizure during the monitoring.

*Sample-size:* We expect a sensitivity of 80% and specificity of 60%. We expect that 50% of the investigated patients will be operated and 66% of them will become seizure-free. Calculating with an accuracy of estimate of 10%, we need 250 patients (Hess et al., Eur J Clin Microbiol Infect Dis (2012)).

*Recordings:* Although there will be variations from center-to-center concerning the EEG electrode array, we will attempt to achieve as much standardization as possible. Centers will use either caps or cup-electrodes (mounted individually).

- a) Caps: need to be of at least 64 electrodes (10-10 system), with even spatial distribution of the electrodes, and including the inferior electrode chain. The centers will specify how they place the cap relative to fiducials and other possible reference visible on the MRI. (For example; how far is the foremost midline electrode away from Nz and the most posterior electrode from Iz; how far is the most lateral inferior electrode away from the lateral eye corner).
- b) Cup-electrodes: we need at least the standardized electrode array of 40-electrodes, described in appendix-1.

Before starting the study, we will discuss with each center the electrode array they use, and we need to validate for the study each array that will be used in the study.

In addition, the centers that have the equipment, high-density EEG (HD-EEG) will be recorded for 1-4 hours at the end of the LTM. Sampling frequency: at least 250 Hz.

The two teams (BESA and Epilog) will mark the six fiducials (T9, T10, Nz, Iz, AC, PC) in the MRI (each team marks it, the other team double-checks).

The centers will annotate in their original EEG format, the following time-points for the seizures:

- Start of the seizure (START), end of the seizure (STOP) defined as follows: Start = first semiological or EEG sign indicating seizure – whichever comes first; Stop = last semiological or EEG sign indicating seizure – whichever comes last.
- The time-limits of a (quasi) artifact-free epoch as close as possible to the electrographic onset, that they suggest being analyzed (EEG-START; EEG-STOP). The epochs should be as long as possible, with a minimum of 3 s: (EEG-start and EEG-stop)

The centers will classify seizures into “types”. A seizure type is a group of seizures that has stereotypical semiology and ictal-EEG. If there are 3 or more seizures in a group (“type”), the centers will annotate at

least 3 seizures for each type, selecting the ones with clearest EEG. All seizures per type are annotated, but maximally 3 seizures per type (in the case of more than 3 choose the best 3).

*Data for source imaging:* After the LTM, centers will upload two de-identified datasets for each patient: EEG (from LTM – all centers; from HD-EEG recordings: selected centers) and MRI (3D T1). For the submission the centers will use the platform developed by Epilog, which is encrypted, HIPAA/GDPR compliant and easy-to-use. BESA will get access to the data uploaded to the Epilog site, and will store data only on drives that are encrypted by Truecrypt. These drives will only be accessible by the persons participating in the study and will be password protected (long string!). One backup will be on our internal server - all encrypted.

For HD-EEG recordings, the coordinate file will also be uploaded by the centers that measure the 3D-positions of the electrodes.

*Additional data provided by the participating centers:* demographic and clinical data (appendix-2), results of the neuroimaging (MRI, PET, SPECT) localization at sub-lobar level (appendix-3), and screen-shots (axial, coronal and sagittal planes) and changes in patient management (appendix-4). These data will not be available for those running the automated source imaging. After the operation: information on the resection, the pathology, postoperative MRI, outcome one year after the operation.

*Automated source imaging:* Epilog and BESA will run the automated source imaging – both for interictal epileptiform discharges (EDs) and ictal signals. A report summarizing the results will be send to the corresponding center and the PI in a one-step procedure.

The automated source imaging consists of 2 phases:

1. Automated detection of EDs
2. Source imaging of each spike cluster and seizure onset epoch.

The complete procedure will be done using automated algorithms without subjective interactions during spike detection and source imaging. For each detected spike cluster and seizure-onset, source imaging will be done at two different time-epochs: at onset and at peak. The two analysis-teams will use two different methods for defining the onset epoch. The time-points (or epochs) for onset and peak will be specified for each spike cluster using the peak channel in the common average montage.

The analysis-teams will provide source images in axial, coronal and sagittal planes. Epilog will use SLORETA for interictal analysis and LORETA followed by functional connectivity analysis for ictal source imaging. BESA will use Multiple Dipole Analysis, Volume- and Cortical-CLARA.

Individual head models will be used for the analyses. BESA will use FEM or an approximate model if the quality of an MRI should be insufficient. Epilog will use a head model with six different tissue classes (scalp, skull, cerebrospinal fluid, gray matter, white matter and air). The finite difference method is used to calculate the lead-fields, which describe the relation between current source in the brain and measured potentials at the electrodes.

Each analysis-team will send a report to the center that submitted the data and to the PI. The report will contain the following:

- Patient code and descriptive data about the recording (duration, number of electrodes)
- Data of up to six clusters in the order of the number of spikes in each cluster
- The minimum number of spikes in a cluster must be 20 spikes

The data of each cluster should contain:

- Number of spikes in each cluster
- Waveforms of 10 examples of spikes
- Averaged waveforms and voltage maps at peak and onset.  
All waveforms (+/-500 ms around the peak) will be provided filtered with a 1 Hz forward low filter and a high filter of 70 Hz both in longitudinal bipolar and common average montages.
- Source images for the two time-points (or epochs): onset and peak (in separate images). Images should be provided in transversal, sagittal and coronal views.
- BESA will also provide source waveforms for onset and peak (only one if not substantially different) and a current vector depicting the orientation of the spike source current.
- The analyzed ictal signal for each seizure-onset epoch in common average montage with marking of the cycles/epoch that has entered the analysis.
- The source images for each seizure-onset epoch.

For the interictal EDs we will use two different definitions of the “dominant” cluster:

- Quantitative definition: the cluster with the highest number of spikes
- Qualitative definition: each center will mark a spike as dominant, in the clinical context (thus not necessarily the most prevalent cluster).

*Reference standard (“gold standard”):* For determining accuracy (sensitivity, specificity, PPV and NPV) and overall accuracy ((TP+TN)/total) gold standard will be the resected site and the outcome one year after the operation:

- TP: source is in the same sub-lobar region as the resection, seizure-free outcome
- FP: source is in the same sub-lobar region as the resection, not seizure-free outcome
- TN: source outside the sub-lobar region that was resected, not seizure-free outcome
- FN: source outside the sub-lobar region that was resected, seizure-free outcome.

To enable an adequate comparison between methods, each method should create an ellipsoid around each center location (maximum of SLORETA, equivalent dipole location(s), seeded center of cortical CLARA / CLARA) indicating the likely error in localization due to electrode/registration inaccuracies and unknown conductivities. The ellipsoid has a larger axis in radial direction (2.5 cm) as compared to the tangential axes (1.8 cm), because of the large effect of the unknown conductivities on source depth.

For determining clinical utility, the percentage of patients in whom ESI changed decision on patient management (appendix-4) will be calculated.

Four centers (Copenhagen, Dianalund, Freiburg and Prague) will do “manual” ESI, as part of the preoperative workup. In this sub-group, the performance of the various pipelines and analysis methods will be compared. The MDTs in these centers will first get access to the “manual” ESI, after scoring the clinical utility for the automated analysis.

*Authorship:*

Principal investigator, guarantor and corresponding author: [name].

Co-authors:

- Epilog team: [name], [name], [name], [name]
- BESA-team: [name], [name], [name], [name]
- From the participating centers: one author per center - provided the center submitted complete datasets for more than 10 patients, including at least 5 operated patients; two authors per center - provided the center submitted complete datasets for more than 20 patients, including 10 operated patients.

**The study protocol will be registered and published at the start of the study. As the goal of the study is to assess the accuracy and clinical utility of ESI methods and not compare products of companies, the results will not be presented as a comparison between companies/products, but as comparison between different analysis methods and strategies.**

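### 250 investigated patients do not give the stated 10% precision for specificity or NPV; the plan's own inputs give about ±15 points at 95% confidence

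*Protocol*

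**What the plan says.** The Protocol's *Primary outcome* paragraph lists "accuracy measures (sensitivity, specificity, positive and negative predictive values), overall accuracy (number of [TP and TN]/total patients").

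The *Sample-size* paragraph gives the expected performance ("We expect a sensitivity of 80% and specificity of 60" per cent), then the expected patient flow: "We expect that 50% of the investigated patients will be operated and 66% of them will become seizure-free". It concludes: "Calculating with an accuracy of estimate of 10%, we need 250 patients". It names no confidence level, does not say whether the 10% is a half-width or a full width, and does not tie it to a particular measure. A published sample-size reference is cited for the calculation.

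The *Reference standard* paragraph fixes who can be counted: "gold standard will be the resected site and the outcome one year after the operation". Two of the four cells show what follows for the denominators: "TN: source outside the sub-lobar region that was resected, not seizure-free outcome" and "FN: source outside the sub-lobar region that was resected, seizure-free outcome". All four cells require a resection and a postoperative outcome, so a patient who is not operated enters none of them.

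**The concern.** The precision of each accuracy measure depends on its own denominator, not on the number enrolled. Specificity is estimated only in operated patients who are not seizure-free, which on the plan's figures is 17% of those investigated (0.50 × 0.34). NPV is estimated only in operated patients whose source lies outside the resected region, a group of nearly the same expected size. One precision figure and one sample size are quoted as if they served the whole primary outcome, although these two denominators are about half the size of those for sensitivity and PPV.

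At stake is what the study can say about cases where surgery failed. Specificity describes how often ESI points away from the resection in those patients. An interval of roughly 45% to 75% around an expected 60% is compatible with quite different conclusions, while readers would believe the study had been sized for ±10.

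**Working it through.** **Inputs (all from the Protocol).** Sensitivity 0.80, specificity 0.60, operated share 0.50, seizure-free share of the operated 0.66, target 10%, N = 250 (*Sample-size*); cell definitions (*Reference standard*). Assumptions added here: two-sided 95% confidence (z = 1.96), and 10% read as a half-width.

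**Step 1. Can 250 be reproduced?** The standard precision formula is n = z²p(1−p)/d², divided by the share of investigated patients who enter the denominator.

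- Sensitivity, d = 0.10: 1.96² × 0.16 / 0.01 = 61.5 seizure-free patients; divided by 0.50 × 0.66 = 0.33, this is 187 investigated (188 if 61.5 is first rounded up to 62).
- Specificity, d = 0.10: 1.96² × 0.24 / 0.01 = 92.2 non-seizure-free patients; divided by 0.50 × 0.34 = 0.17, this is 543 investigated (about 547 if first rounded up to 93).
- Other readings, as investigated patients needed:

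| Reading | Sensitivity | Specificity |
|---|---|---|
| 90% confidence, ±10 | 131 | 382 |
| 80% confidence, ±10 | 80 | 232 |
| 95%, 10% as full width (d = 0.05) | 745 | about 2,170 |
| 95%, ±10, no allowance for the operated share | 93 | 271 |

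None of these gives 250, so the stated figure is not reproduced. The cited reference was not available for this check.

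**Step 2. What 250 delivers.**

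- Operated: 250 × 0.50 = 125
- Seizure-free: 125 × 0.66 = 82.5; not seizure-free: 42.5
- TP = 82.5 × 0.80 = 66; FN = 16.5
- TN = 42.5 × 0.60 = 25.5; FP = 17

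Half-width = z × √(p(1−p)/n):

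| Measure | Expected value | Denominator | 95% | 90% |
|---|---|---|---|---|
| Sensitivity | 80% | 82.5 | ±8.6 | ±7.2 |
| PPV | 66/83 = 79.5% | 83 | ±8.7 | ±7.3 |
| Overall accuracy | 91.5/125 = 73.2% | 125 | ±7.8 | ±6.5 |
| Specificity | 60% | 42.5 | **±14.7** | ±12.4 |
| NPV | 25.5/42 = 60.7% | 42 | **±14.8** | ±12.4 |

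For overall accuracy, total patients is taken as the 125 who can be classified.

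**Step 3. Does the result depend on the method or on chance?**

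- For 26 of 43, the exact 95% interval is 44.4% to 75.0% and the Wilson interval 45.6% to 73.6%.
- If the number of non-seizure-free patients is also allowed to vary (binomial, 250 at 0.17), the specificity half-width falls between about 12.5 and 17.1 points in the central 95% of outcomes. The chance that it is 10 points or less is below 0.01%.
- A half-width of 10 points with 42.5 patients corresponds to a confidence level of about 82%.

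**Step 4. If 250 meant operated patients.** Then 250 × 0.34 = 85 are not seizure-free and the specificity half-width is 1.96 × √(0.24/85) = 10.4 points. That is close to the target, but the text applies the 50% to investigated patients, so it is not the design as written.

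**Step 5. Losses.** The paragraph makes no allowance for operated patients without a usable ESI result or a one-year outcome. As an assumption, if 10% or 20% of operated patients were lost, 38.25 or 34 non-seizure-free patients would remain, with half-widths of ±15.5 or ±16.5 points.

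**The case against.** The protocol never says in terms that all the measures reach 10%. Sensitivity and specificity are the only accuracy inputs it gives, and no PPV or NPV is anticipated, so holding NPV to the 10% is an inference. Three of the five primary measures do meet the target. No confidence level is stated and the cited method could not be consulted. No hypothesis test or threshold for specificity is set, so a wide interval breaches no decision rule, and the reported intervals will show the true precision in any case.

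Some of this stands. Specificity is the firm part of the finding, since it is an explicit input; NPV follows because it belongs to the same primary outcome and the 10% is stated without restriction. It is fair to record that overall accuracy meets the target. With no benchmark set, the consequence is best described as imprecision and not as a failure against a threshold. The point on losses is a supporting one. The rule in the list of report contents, "The minimum number of spikes in a cluster must be 20 spikes", concerns interictal clusters, and a patient without such a cluster may still have an ictal result.

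None of it rescues the 250. The shortfall remains at 90% confidence, and sizing for sensitivity alone would give about 187. The error lies in a claim the protocol itself makes, so it is not a detail left to a later analysis plan.

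**Conclusion.** The concern holds. With the protocol's own inputs, 250 investigated patients give 95% half-widths of 14.7 points for specificity and 14.8 for NPV, about half as wide again as the stated 10. Sensitivity, PPV and overall accuracy are within 10 points. The conclusion rests on reading 10% as a half-width and on 95% confidence, neither of which the protocol states. It survives a change to 90%, and a full-width reading makes the shortfall larger. Only a confidence level of about 82% or lower would bring specificity to ±10. Because the misstatement concerns the design precision of two primary measures, it should be corrected.

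**What to change.** Keep 250 and replace the precision claim. Suggested wording:

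> With 250 investigated patients (125 operated, about 82 seizure-free and about 42 not), the expected half-widths of the 95% confidence intervals are about ±9 points for sensitivity and PPV, ±8 points for overall accuracy and ±15 points for specificity and NPV, before any loss through unusable ESI or missing one-year outcome.

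State the confidence level and remove the unqualified 10%. If 250 was intended as the number of operated patients, say so and correct the enrolment figure: at 50% operated that means 500 investigated, with specificity at ±10.4. If ±10 for specificity is a real requirement, about 543 to 547 investigated patients are needed.

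Restating the precision costs one paragraph and no extra patients; the only price is a less favourable stated precision for two measures.

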### **Appendix-3: The sub-lobar regions**

See the CRF for more details.

Side: left / right

Regions:

- Frontal
  - perisylvian-superior surface / operculum
  - lateral
  - mesial
  - polar
  - orbitofrontal
- temporal
  - mesial
  - polar
  - basal
  - lateral-anterior
  - lateral-posterior
  - perisylvian-inferior surface / operculum
- central
  - lateral convexity
  - mesial
  - central sulcus – anterior surface
  - central sulcus – posterior surface
  - perisylvian-superior surface / opercular
- parietal
  - lateral-convexity
  - mesial

- perisylvian-superior surface / opercular
- occipital
  - lateral
  - mesial
  - basal
- insula

**Appendix-4:** Logging the changes in decision on clinical management of the patients:

The multidisciplinary teams take decisions in two steps:

- I. Considering all data, except ESI
- II. Adding ESI to all other data.

At each step, the decisions are classified into one of the following categories:

1. Stop (operation not recommended)
2. Implantation of intracranial electrodes
3. Operation

In addition, the changes are classified into one of the following categories:

1. No change – but concordant with decision.
2. No change – but discordant with decision.
3. Change from stop to implantation.
4. Change from implantation to stop.
5. Change in implantation plan: implantation of additional sites (besides the ones planned in step-1).
6. Change from implantation to operation.
7. Change from operation to implantation.
8. Other (specify in free text).

If changes are not related to all analyses results, it will be noted, which method(s) triggered the change (SLORETA-interictal / ictal; ECD-interictal/ictal; CLARA interictal/ictal).

At one-year follow-up, the changes are categorized as useful or not useful. A change is defined useful as follows: (a) change from stop to ICR: the ICR localized the source; (b) change in implantation strategy: the electrode(s) implanted based on the EMSI identified the source; (c) change from implantation to operation: the patient became seizure-free.

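### The resection that serves as reference standard is chosen after the team has seen ESI, and Appendix-4 as shown records the pre-ESI target too thinly to measure the resulting dependence fully

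*Protocol*

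**What the plan says.** The Reference standard paragraph of the protocol states that for accuracy the "gold standard will be the resected site and the outcome one year after the operation". All four cells of the 2x2 table depend on whether the source lies in the resected sub-lobar region.

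Under Automated source imaging: "Each analysis-team will send a report to the center that submitted the data and to the PI". Appendix-4 has the team decide first without ESI and then a second time: "Adding ESI to all other data". The protocol expects ESI to be acted on. One of its definitions of a useful change is that "the electrode(s) implanted based on the EMSI identified the source".

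On what is logged, Appendix-4 says: "At each step, the decisions are classified into one of the following categories". The categories are stop, implantation and operation. Among the eight change codes, code 5 concerns sites: "Change in implantation plan: implantation of additional sites (besides the ones planned in step-1". Code 8 is the residual: "Other (specify in free text". Codes 1 and 2 split the no-change cases into concordant and discordant. Where a change does not rest on all the analyses, the method that triggered it is noted.

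Elsewhere, centers supply "results of the neuroimaging (MRI, PET, SPECT) localization at sub-lobar level (appendix-3", and Appendix-2 codes the location of the resection actually done.

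**The concern.** Accuracy is the primary outcome. If the team moves a resection towards the ESI source, that source becomes concordant with the resection because it was followed, not because it was independently confirmed. A patient who would have been FN or TN becomes TP or FP. For the source followed, FN and TN shrink, so apparent sensitivity rises and apparent specificity falls. If ESI never alters the site, there is no bias by this route.

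The only blinding stated keeps clinical data from the ESI analysts. It does not keep ESI from influencing the resection.

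The dependence could be measured if the team's target were on record before ESI was seen. The imaging regions are only a proxy for that target: Appendix-2 allows MRI, PET and SPECT to be normal, and they may disagree with one another. A target not recorded at the time cannot be fully reconstructed later.

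**Working it through.** **What the fields recover**

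| Situation | Recoverable from Appendix-4 as shown? |
|---|---|
| Change between stop, implantation and operation | Yes, category at each step |
| Added implantation sites | Yes, code 5 |
| No change, ESI agrees or disagrees with the decision | Yes, codes 1 and 2 |
| Which method triggered a change | Yes, when not all analyses did |
| Operation at both steps, moved to another region | Not by a code of its own; could be logged as no change or as free-text other |
| Sub-lobar target at step I | Not listed |

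**Base table.** This point disputes no stated figure. The inputs are from the Sample-size paragraph: 250 patients, 50% operated, 66% of those seizure-free, sensitivity 80%, specificity 60%.

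- Operated: 250 × 0.50 = 125. Seizure-free: 125 × 0.66 = 82.5. Not seizure-free: 42.5.
- TP = 0.8 × 82.5 = 66; FN = 16.5; TN = 0.6 × 42.5 = 25.5; FP = 17.
- Discordant resections: 16.5 + 25.5 = 42. PPV = 66/83 = 79.5%. Overall accuracy = 91.5/125 = 73.2%.
- 95% half-widths (confidence level assumed): 1.96 × √(0.16/82.5) = 8.6 points for sensitivity; 1.96 × √(0.24/42.5) = 14.7 points for specificity.

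**Steering model (assumed).** A share m of the 42 discordant resections is moved into the ESI region, equally from FN and TN. A share s of the moved patients becomes seizure-free. The planned 80% and 60% are treated as free of steering.

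- TP = 66 + 42ms; FP = 17 + 42m(1 − s); FN = 16.5(1 − m); TN = 25.5(1 − m).
- Two intermediate values of s: 0.66, the plan's seizure-free share, and 0.795, the base PPV.

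| m (patients moved) | s | Sensitivity | Specificity |
|---|---|---|---|
| 10% (4.2) | 0.66 | 68.77/83.62 = 82.2% | 22.95/41.38 = 55.5% |
| 10% (4.2) | 0.795 | 82.4% | 56.2% |
| 20% (8.4) | 0.66 | 71.54/84.74 = 84.4% | 20.40/40.26 = 50.7% |
| 20% (8.4) | 0.795 | 84.6% | 52.1% |
| 30% (12.6) | 0.66 | 74.32/85.87 = 86.5% | 17.85/39.13 = 45.6% |
| 30% (12.6) | 0.795 | 86.8% | 47.7% |

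Sensitivity rises by 2.2 to 6.8 points and specificity falls by 3.8 to 14.4 points. At 20% steering, overall accuracy is (71.54 + 20.40)/125 = 73.6% for s = 0.66 and 74.5% for s = 0.795, against 73.2%. The summary figure hardly moves while its components shift in opposite directions.

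**Extreme outcomes.** If every moved patient keeps the original outcome, 30% steering gives a specificity of 25.5 × 0.7/42.5 = 42.0%, a fall of 18 points. If no moved patient becomes seizure-free, 20% steering gives 20.4/(42.5 + 3.3) = 44.5% and 30% gives 17.85/(42.5 + 4.95) = 37.6%. Only such assumptions take the fall past 14.7 points.

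**The case against.** The strongest reply is that disclosure is not a fault. Clinical utility cannot be measured unless the team sees ESI. That stands, and it rules out the tempting reading that the team should have been kept blind or that the accuracy results are invalid.

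Second, much is already recorded: category at each step, concordance codes, added sites, free text and the triggering method. Codes 1, 2 and 5 presuppose some notion of what step I had planned. The CRFs, to which Appendices 2 and 3 refer, are not at hand and might hold a target field. This limits the point to what Appendix-4 lists; a reader should not infer that no target is written down anywhere. It does not close the gap, because a moved operation could still be logged as no change.

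Third, several methods, two time points and up to six clusters are evaluated. A resection drawn towards one source may be drawn away from another, so the direction given above does not hold for every method. That stands.

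Fourth, a target recorded at step I helps mainly patients already heading for operation. Those at stop or implantation may have no settled target. That also stands and limits what the fix can deliver.

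Finally, the analysis and its caveat could sit in a SAP that is not shown. That is fair, but no SAP can supply a field that was not collected.

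**Conclusion.** The accuracy table is not independent of the index test, and the fields listed in Appendix-4 capture that dependence only in part. The severity is minor to moderate.

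The size is unknown, because the protocol does not say how often ESI moves a resection. The illustrated shifts of about 4 to 14 points in specificity and 2 to 7 in sensitivity rest on the assumed 10–30% steering, on 66–79.5% of moved patients becoming seizure-free, on equal steering of FN and TN, and on the planned 80% and 60% being free of steering. They apply to the source the team follows.

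A reader might infer that specificity is distorted beyond its sampling error. The documents do not support that. It arises only in the extreme cases: no moved patient becomes seizure-free, or moving a resection never alters outcome, which would mean that seizure-free patients would have been so with either region resected. Under the intermediate assumptions both shifts stay inside the half-widths. They are nevertheless systematic, so a larger sample would not remove them.

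**What to change.** (a) In Appendix-4, record the Appendix-3 code or codes of the presumed target, or an entry for not yet defined, at step I before the automated report is opened and again at step II. Add a change code for a changed planned resection site. If the CRFs already hold such a target field, cite it in Appendix-4; only the change code is then needed. This item must be in place before data are collected.

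(b) As a sensitivity analysis, report accuracy per method in operated patients without an ESI-triggered change in category, implantation plan or target. Report also the concordance of ESI with the step-I target where one was defined. Note that this stratum is selected, and that the teams in four centers also see manual ESI after scoring the automated analysis, a further route of influence.

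(c) State that the pooled accuracy figures are not independent of ESI. Items (b) and (c) may be placed in the SAP.

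The cost is a target entry at each of two steps and one extra change code, with no added patients or procedures. Intervals widen in the no-change stratum. If 10, 20 or 30% of operated patients had a change (assumed), 112.5, 100 or 87.5 remain. With the same expected proportions, the 95% half-widths are about 9.1, 9.7 or 10.3 points for sensitivity and 15.5, 16.5 or 17.6 for specificity.

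### Only operated patients enter the accuracy table, and ESI helps decide who is operated, so verification depends on the index test

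*Protocol*

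**What the plan says.** The Goal and Primary outcome paragraphs make sensitivity, specificity, predictive values and overall accuracy of ESI in presurgical evaluation the main result. The Reference standard paragraph fixes how a patient is classified: "gold standard will be the resected site and the outcome one year after the operation". All four cells need both parts of that standard. The two test-negative cells, for example, read "FN: source outside the sub-lobar region that was resected, seizure-free outcome" and "TN: source outside the sub-lobar region that was resected, not seizure-free outcome".

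ESI is not withheld from the treating team. The Automated source imaging paragraph says: "Each analysis-team will send a report to the center that submitted the data and to the PI". Appendix-4 has the team decide twice, the second time after "Adding ESI to all other data". The step-II decision is evidently acted on, because usefulness is scored from what followed, for instance "change from implantation to operation: the patient became seizure-free".

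The change list in Appendix-4 includes "Change from implantation to stop" (category 4) and "Change from operation to implantation" (category 7). It also lists changes towards surgery: stop to implantation (category 3) and implantation to operation (category 6). Operation to stop has no category and would fall under the free-text one. Appendix-2 asks for a resection location only in operated patients. Appendix-4, as shown, records the class of the step-I decision but no target region.

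**The concern.** In an accuracy study, the result of the test under study should not influence who receives the reference standard. Here it can. A patient taken out of surgery because of ESI has no resection and no postoperative outcome, so he or she falls out of the primary analysis. The protocol does not mention this and presents the operated-only figures as the accuracy of ESI in presurgical evaluation.

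If the patients who leave are mainly those whose source disagrees with the surgical hypothesis, the test-negative cells (FN and TN) are under-filled. Sensitivity then looks better and specificity worse than in the candidates as a whole. A larger sample would not cure this. Appendix-4 also gives no usefulness criterion for a change from implantation to stop, so such a patient is assessed for neither accuracy nor usefulness.

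**Working it through.** **Inputs (Sample-size paragraph).** Sensitivity 0.80, specificity 0.60, 50% operated, 66% of those seizure-free, 250 patients. The documents give no rate at which ESI moves patients in or out of surgery, so the ratio r below is an assumption.

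**Planning table.** 250 × 0.50 = 125 operated; 125 × 0.66 = 82.5 seizure-free and 42.5 not. This gives TP 66, FN 16.5, TN 25.5, FP 17. PPV = 66/83 = 79.5%, NPV = 25.5/42 = 60.7%, overall accuracy = 91.5/125 = 73.2%. If the total in overall accuracy meant all recruited patients, it would be 91.5/250 = 36.6%, so the denominator needs stating.

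**Selection by concordance.** Let r be the chance of operation with the source outside the intended target, divided by the chance with the source inside. Suppose it is the same in would-be seizure-free and not seizure-free patients, and treat 80%/60% as the values before selection. Then

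- crude sensitivity = 0.8 / (0.8 + 0.2r)
- crude specificity = 0.6r / (0.6r + 0.4)

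| r | Sensitivity | Specificity |
|---|---|---|
| 1 (equal removal) | 80.0% | 60.0% |
| 0.9 | 0.8/0.98 = 81.6% | 0.54/0.94 = 57.4% |
| 0.7 | 0.8/0.94 = 85.1% | 0.42/0.82 = 51.2% |
| 0.5 | 0.8/0.90 = 88.9% | 0.30/0.70 = 42.9% |

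At r = 0.7 overall accuracy is (66 + 17.85)/(66 + 11.55 + 17.85 + 17) = 83.85/112.4 = 74.6%. PPV and NPV do not change under this pattern.

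**Other patterns.**

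- 30% of source-inside and 10% of source-outside patients leave (r = 0.9/0.7): 75.7% and 65.9%, the reverse direction.
- Only TN patients leave (30%): sensitivity stays at 80%, specificity 51.2%, NPV 52.0%.
- Only FN patients leave (30%): sensitivity 85.1%, specificity stays at 60%, NPV 68.8%.
- 30% of source-outside patients are diverted, but half of these are resected later with the source still outside: sensitivity goes from 83.1% to 79.3% and specificity from 56.7% to 52.1% as the seizure-free rate of those who return goes from 0.3 to 0.9.
- 10 or 20 source-inside patients are added by changes towards surgery, 66% seizure-free: 81.5%/55.6% or 82.8%/51.7%.

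**What a correction needs.** If operation depends only on concordance, PPV and NPV among the operated are valid, and corrected sensitivity = c·PPV / [c·PPV + (1 − c)(1 − NPV)], where c is the share concordant among all candidates. With c = 83/125 = 0.664, this is 0.528/(0.528 + 0.132) = 80%. Specificity is likewise 0.204/(0.204 + 0.136) = 60%. The correction works only if c can be counted in unoperated patients. The protocol defines concordance against the resected region, which they do not have.

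**The case against.** A reader might infer three stronger things, and the documents support none of them.

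- *That every patient in categories 4 and 7 drops out.* Category 7 patients may be resected after intracranial recording and then classified. Only those never resected leave. Operation to stop is not a listed change. The category for no change despite discordance shows that the protocol also expects some discordant patients to stay on course.
- *That sensitivity is certainly inflated and specificity certainly deflated.* The protocol does not say why a patient would be stopped, and a category 4 patient had an implantation plan at step I, not a resection plan. The patterns above include no shift, a shift in one measure only, and a reversal.
- *That a standard verification correction can be run on what is already logged.* It cannot, because an unoperated patient has no test result as the protocol defines it.

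Three further objections deserve weight. The planning values describe operated patients, so using them as values before selection is only illustrative; at r = 0.7 the operated seizure-free share becomes 77.55/112.4 = 69%, not 66%. At r = 0.7 the shifts of 5.1 and 8.8 points lie within the 95% half-widths expected at 250 patients (8.6 and 14.7 points). Unoperated patients have no postoperative outcome in any design, and stratified or corrected analyses can be left to an analysis plan.

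All three limit the size of the point, not the mechanism. Bias and sampling error are different things, and an analysis plan cannot later supply a target region that was not recorded.

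**Conclusion.** The point holds as a cheap improvement. On the text, ESI is disclosed before the decision that determines who is operated, and only operated patients can be classified. Crude sensitivity, specificity and overall accuracy therefore describe patients operated with ESI known, not all candidates in presurgical evaluation.

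The upward shift in sensitivity and downward shift in specificity are conditional on source-outside patients being operated less often than source-inside ones within each outcome group. The size is unknown. Under the assumed ratios of 0.9 to 0.5 it runs from 1.6 to 8.9 points for sensitivity and from 2.6 to 17.1 points for specificity. PPV and NPV are unaffected only if, given concordance, operation does not depend on the would-be outcome.

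**What to change.** 1. In Appendix-4, record for every patient the presumed target region at step I, using the Appendix-3 codes and allowing an entry for no single target. ESI concordance is then defined per method in unoperated patients too. Give operation-to-stop its own change code. If the CRF, which is not at hand, already holds the region, the protocol need only say so.
2. In the Reference standard paragraph, state that crude sensitivity, specificity and overall accuracy apply to patients operated with ESI known, and that the total is the number of classified operated patients.
3. Tabulate operated and not operated by step-I decision, step-II decision and ESI concordance with the step-I target.
4. As a sensitivity analysis on that step-I concordance, give verification-corrected sensitivity and specificity within step-I strata. Add bounds that vary the would-be outcome of unoperated patients and do not assume that everyone who leaves is test-negative. Among operated patients, show how often the step-I target matches the resected region.

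The cost is one CRF field, one code and a short secondary analysis, with no extra patients or procedures. The downside is a second, wider pair of estimates. They rest on the assumption that, given step-I decision and concordance, being operated does not depend on the would-be outcome.
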